g. If pembrolizumab is permanently discontinued first and the day 90 safety follow-up visit after the last dose of pembrolizumab falls into the regorafenib treatment period or regorafenib day 30 safety follow-up period, no separate pembrolizumab day 90 safety follow-up visit is necessary as the information gathering and examinations will occur with regorafenib treatment cycle visit, EoT visit, or day 30 safety follow-up visit (required for either regorafenib, pembrolizumab, or combination). All pregnancies and exposure during breastfeeding should be collected from the start of study intervention through 120 days following discontinuation of study intervention, or 30 days following discontinuation of study intervention if the participant initiates new anti-cancer therapy

h. Every 6 weeks (±7 days) until PD during the first 54 weeks of treatment; every 9 weeks (±7days) until PD afterwards

i. Study intervention-related AEs only

j. Optional; however, Panel A is required on W1D1 if screening tests were not completed within 7 days of first study intervention.

08 JUN 2021 Page 24 of 141

1.3.2 **Biomarker Sampling**

Table 1-2: Schedule of Biomarker Blood Sampling

	Scree	ening				Inte	rvent	tion F	Perio	d (we	eks)ª				End of treatment (DC)
Procedure	Within 28 days prior to the first dose	Within 7 days prior to the first dose	W1 D1	W2 D1	W3 D1	W4 D1	W5 D1	W6 D1	W7 D1	W8 D1	W9 D1	W13 D1	W19 D1	W25 D1	Within 14 days after last dose or DC decision (DC of both rego and pembro)
								± 3	days	,					+ 7 days
Whole blood for pharmacogenetics			Х												
Biomarker blood for flow cytometry 1 ^b		Х	Х	х			Х		Х		Х	Х	Х	Х	Х
Biomarker blood for flow cytometry 2 ^b		Х	Х	Х			Х		Х		Х	х	Х	Х	Х
Biomarker serum		Х	Х	Х			Х		Х		Χ	Х	Х	Х	Х
Biomarker plasma		Х	Х	Х			Х		Х		Х	Х	Х	Х	Х
Biomarker plasma for ctDNA		Х	X				Х		Х			х	Х	х	Х

ctDNA = circulating tumor deoxyribonucleic acid; D = day; DC = discontinuation of study intervention; pembro = pembrolizumab; W = week(s)
a: All samples are to be collected pre-dose.
b. Blood will be collected for flow cytometry from participants enrolled in the expansion phase only, and may only be collected in a subset of participants.

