Participants will receive study intervention until tumor progression, unacceptable toxicity, withdrawal of consent, investigator's decision to stop therapy for the participant, sponsor's decision to terminate the study, or death. If in the opinion of the investigator, the participant may still derive clinical benefit despite disease progression, continuation of study intervention is permitted after discussion with the sponsor.

At the investigator's discretion, a participant may continue on study intervention beyond radiological progression as defined by RECIST 1.1 if the clinical condition of the participant is stable or the participant is improving symptomatically, and the investigator expects continued clinical benefit for the participant until subsequent progression determined by iRECIST criteria (see Section 7.1).

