7.1.1 Withdrawal Criteria

7.1.1.1 Withdrawal from Study Intervention Period

Participants MUST be withdrawn from the study intervention if any of the following occurs:

- At their own request or at the request of their legally acceptable representative (if acceptable by local law). At any time during the study and without giving reasons, a participant may decline to participate further. The participant will not suffer any disadvantage as a result.
- If, in the investigator's opinion, continuation of the study intervention would be harmful to the participant's well-being.
- Progressive disease as per RECIST 1.1; however, treatment beyond radiological progression per iRECIST is possible if the participant is still benefiting from treatment.
- Clinical progression (every effort should be made to obtain radiological confirmation of disease progression [PD] during active follow-up). Note: In cases where radiographic evaluation is not possible, clinical progression may be used. Clinical progression is based on the judgment of the investigator (e.g., defined as worsening of the ECOG PS ≥3 or symptomatic deterioration including increase in liver function tests).
- The development of a second primary malignancy that requires a different treatment.
- Development of any intercurrent illness or situation which may, in the judgment of the investigator, affect assessments of clinical status and study endpoints to a relevant degree.
- Severe allergic reactions, such as exfoliate erythroderma, anaphylaxis, or vascular collapse.
- Start of a new anti-cancer therapy.

Page 77 of 141

- Use of illicit drugs or other substances that may, in the opinion of the investigator or their designated associate(s), have a reasonable chance of contributing to toxicity or otherwise confound the results.
- Pregnancy.
- Participant lost to follow-up.
- Death.

Participants MAY be withdrawn from the study intervention for the following reasons:

- At the specific request of the sponsor and in liaison with the investigator (e.g. obvious non-compliance, safety concerns).
- Participants should be taken off study intervention for disease progression. However,
 if a participant has radiographic progression but is achieving a clinically meaningful
 benefit, an exception to continue study intervention may be considered following
 consultation with the sponsor.

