If bone metastases are known or suspected, a whole-body bone scan with both anterior and posterior projection using a technetium-99m-labeled phosphonate tracer (methylene diphosphonate (MDP), hydroxymethylene diphosphonate (HMDP), hydroxyethylene diphosphonate (HDP), or 2,3-dicarboxypropane-1,1-diphosphonate (DPD)) should be performed at screening. Bone scans should be repeated when CR or PR is identified in the CT/MRI assessments to confirm the absence of new bone lesion(s) disease or when progression in bone is suspected. A newly-detected bone lesion on bone scan should be confirmed by radiologic assessment (X-ray, CT, MRI if not already evident on the CT/MRI tumor assessment scans).

For consistency, the same imaging modality and equivalent technique (e.g. contrast agent, slice thickness, field of view, protocol, sequence, phosphonate tracer) should be used for all scans and tumor assessments across all time points performed on an individual participant, including screening/baseline scans.

Initial tumor imaging:

The time points for CT/MRI scans are described in the SoA (Section 1.3.1). A baseline radiological tumor assessment will be conducted within 28 days before the start of study treatment. Scans performed as standard of care that were obtained prior to the participant signing the informed consent may be used for the baseline tumor assessment, provided that they were performed within 42 days of starting study intervention and meet this protocol's imaging requirements. The investigator must review screening images to confirm the participant has measurable disease per RECIST 1.1 and to determine this participant's eligibility.

Tumor imaging on study:

Following treatment initiation, regardless of potential dose delays for either drug, subsequent tumor assessments will occur every 6 weeks with a maximum window of \pm 7 days during the first 54 weeks and every 9 weeks \pm 7 days thereafter.

Page 82 of 141

For participants who discontinue study treatment without confirmed radiological disease progression, the investigator should perform a complete physical, laboratory, and radiological assessment as soon as possible. Every effort should then be made to continue to perform tumor assessments every 6 weeks \pm 7 days during the first 54 weeks and every 9 weeks \pm 7 days thereafter. Imaging assessments will continue to be performed until whichever of the following occurs first:

- Investigator-assessed disease progression is confirmed

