9.4.1.2 Primary Efficacy Endpoint

The primary endpoint of the study is ORR based on RECIST 1.1 assessed by central review. ORR is defined as the proportion of participants with best overall response of confirmed CR or PR. Participants for whom best overall tumor response is not CR or PR, as well as participants without any post-baseline tumor assessment will be considered non-responders.

In both study phases, the primary efficacy variable will be analyzed after all participants are available for efficacy. The analysis will be done on the Full Analysis Set. In the pilot phase, the analysis will be done by cohort. In the expansion phase, the analysis will be done on the participants who received the first line treatment determined in the pilot phase of the study.

Methods used will include frequency tables (with the ORR table also including all "Best overall response" categories) as well as 95% two-sided Clopper-Pearson confidence intervals and the results of an exact binomial test.

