Target Lesions: All measurable lesions up to a maximum of 2 lesions per organ and 5 lesions in total, representative of all involved organs should be identified as *target lesions* and be recorded and measured at baseline. These 5 lesions should be selected on the basis of their size (lesion with the longest diameter), be representative of all involved organs and should be suitable for reproducible repeated measurements. A sum of the diameters (longest for non-nodal lesions, short axis for nodal lesions) for *all target lesions* will be calculated and reported as the baseline sum diameters. If lymph nodes are to be included in the sum, then as noted above, only the short axis is added into the sum. The baseline sum diameters will be used as reference to further characterize any objective tumor regression of the measurable dimension of the disease. If there are >5 measurable lesions, those not selected as *target lesions* will be considered together with non-measurable disease as *non-target lesions*.

Non-target Lesions: All non-measurable lesions (or sites of disease) plus any measurable lesions over and above the 5 listed as *target lesions*, including pathological lymph nodes (with short axis ≥10 mm and < 15 mm) should be identified as non-target lesions and should also be recorded at baseline. Measurements are not required but these lesions should be noted at baseline and should be followed as "present", "absent" or in rare cases "unequivocal progression". In addition, it is possible to record multiple non-target lesions involving the same organ as a single item on the eCRF (e.g.; 'multiple enlarged pelvic lymph nodes' or 'multiple liver metastases').

Best Response

The best overall response is the best response recorded from the start of the study intervention until the end of intervention. The participant's best overall response assignment will depend on the findings of both target and non-target disease and will also take into consideration the appearance of new lesions. While some non-target lesions may actually be measurable, they need not be measured and instead should be assessed only qualitatively at the time points specified in the protocol.

All participants will have their best response on study classified as outlined below:

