using iRECIST for participant management (see Table 10–11 and Figure 10–1). This decision by the investigator should be based on the participant's overall clinical condition.

Clinical stability is defined as the following:

- Absence of symptoms and signs indicating clinically significant progression of disease
- No decline in ECOG performance status
- No requirements for intensified management, including increased analgesia, radiation, or other palliative care

Any participant deemed **clinically unstable** should be discontinued from study intervention at site-assessed first radiologic evidence of PD, and is not required to have repeat tumor imaging for confirmation of PD by iRECIST.

If the investigator decides to continue treatment, the participant may continue to receive study intervention and the tumor assessment should be repeated 4 to 8 weeks later to confirm PD by iRECIST, per investigator assessment.

Tumor flare may manifest as any factor causing radiographic progression per RECIST 1.1, including:

- Increase in the sum of diameters of target lesion(s) identified at baseline to ≥20% and ≥5 mm from nadir
- Note: the iRECIST publication uses the terminology "sum of measurements", but "sum of diameters" will be used in this protocol, consistent with the original RECIST 1.1 terminology
- Unequivocal progression of non-target lesion(s) identified at baseline
- Development of new lesion(s)

iRECIST defines new response categories, including iUPD (unconfirmed progressive disease) and iCPD (confirmed progressive disease). For purposes of iRECIST assessment, the first visit showing progression according to RECIST 1.1 will be assigned a visit (overall) response of iUPD, regardless of which factors caused the progression.

At this visit, target and non-target lesions identified at baseline by RECIST 1.1 will be assessed as usual.

New lesions will be classified as measurable or non-measurable, using the same size thresholds and rules as for baseline lesion assessment in RECIST 1.1. From measurable new lesions, up to 5 lesions total (up to 2 per organ), may be selected as New Lesions – Target. The sum of diameters of these lesions will be calculated, and kept distinct from the sum of diameters for target lesions at baseline. All other new lesions will be followed qualitatively as New Lesions – Non-target.

Assessment at the Confirmatory Imaging

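### The best-overall-response window behind the primary RECIST 1.1 ORR has no stop at first PD, so as written a confirmed response after a reversed target-lesion PD counts as a primary response

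*Protocol*

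**What the plan says.** **Endpoint.** Protocol 9.4.1.2: "The primary endpoint of the study is ORR based on RECIST 1.1 assessed by central review", and "ORR is defined as the proportion of participants with best overall response of confirmed CR or PR". SAP v3.0 section 5.3.1 restates this definition without a time window and, in 5.3.2, sends the analytical approach to SAP v2.0.

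**Window.** The only window given for RECIST 1.1 best overall response is in Protocol 10.5.1 (Best Response): "The best overall response is the best response recorded from the start of the study intervention until the end of intervention".

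**Response at a visit.** In 10.5.1, PR is judged against the baseline sum and PD against the smallest sum on study. Table 10-5 combines target, non-target and new-lesion findings one visit at a time.

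**Treatment and imaging after PD.** Section 6 says that "a participant may continue on study intervention beyond radiological progression as defined by RECIST 1.1 if the clinical condition of the participant is stable". Section 7.1.1.1 makes PD a reason for withdrawal but adds that "treatment beyond radiological progression per iRECIST is possible if the participant is still benefiting from treatment". The Schedule of Activities plans scans "until PD during the first 54 weeks of treatment". Section 10.5.3 and Table 10-11 keep scheduled imaging going when a repeat scan does not confirm PD. For participants who stop treatment without confirmed radiological PD, one of the events in 8.1 that ends imaging is "Investigator-assessed disease progression is confirmed".

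**Reversed PD.** Section 10.5.3 treats it as pseudo-progression that resolves to iSD, iPR or iCR. Section 3 lists iRECIST ORR as exploratory and by investigator.

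**The concern.** A best-response window that closes at end of intervention equals one that closes at PD only if treatment always stops at PD. Here it need not, for two reasons. The protocol expressly allows treatment beyond RECIST 1.1 progression. And where it names who calls the PD that stops treatment or imaging, it names the site or the investigator; section 10.5.3, for instance, says a clinically unstable participant "should be discontinued from study intervention at site-assessed first radiologic evidence of PD". The primary ORR is read centrally. A central PD that the site reads as SD leaves the window open without anyone deciding to treat past progression.

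A post-progression response, which the protocol places in an exploratory endpoint, can then also enter the primary one. The same participant's duration of response would start after their first PD, although 9.4.1.3 runs it from response to progression.

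The exposure is mainly to PD called on the target-lesion sum. PR requires no new lesions and no unequivocal non-target progression, so a visit at which either persists stays PD.

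**Working it through.** **1. The plan's own figures.** Section 9.2 sets success rules of 27/93 and 34/119 against a 20% null at one-sided 0.025. The exact binomial tails are P(X≥27 | 93, 0.20) = 0.0238 and P(X≥34 | 119, 0.20) = 0.0158. One responder fewer gives 0.0408 (26/93) and 0.0264 (33/119), so both rules are correct minima. The sample-size arithmetic is sound; the issue is what counts as a response.

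**2. Worked case, central sums.** The thresholds come from 10.5.1. PR is at least 30% below baseline. PD is at least 20% and at least 5 mm above the smallest sum. Section 8.1 requires confirmation at least 4 weeks later. Assume stable non-target disease, no new lesions and treatment ongoing.

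| Week | Sum (mm) | Against baseline | Against smallest earlier sum | Visit response |
|---|---|---|---|---|
| 0 | 100 | – | – | – |
| 6 | 72 | −28% | −28% | SD |
| 12 | 87 | −13% | 87/72 = +20.8%, +15 mm | PD |
| 18 | 69 | −31% | below 72 | PR |
| 24 | 68 | −32% | below 69 | PR, confirmed 6 weeks later |

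- Window as written: best response is confirmed PR, a primary responder.
- Window closed at first PD: best response is SD if the week-6 scan meets the 6-week minimum, otherwise PD. Either way the participant is a non-responder.
- iRECIST: the PD threshold is 72 × 1.2 = 86.4 mm. Since 69 < 86.4, iUPD at week 12 resolves to iPR at week 18.
- DOR: it would start at week 18, which is 6 weeks after the central PD.

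**3. Central–site discordance.** If the site measures 86 mm at week 12 against the same smallest sum, 86/72 = +19.4%. The site records SD and treatment continues as usual.

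**4. A case away from the threshold.** Sums of 100, 125 (+25%, +25 mm: PD), 68 (−32%: PR) and 66 at least 4 weeks later (−34%: confirmed) give a responder as written and best response PD under a first-PD cut. If the site also calls this PD, the case needs a decision to treat beyond progression.

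**5. Effect of one participant.** 1/26 = 3.8 points, 1/52 = 1.9, 1/93 = 1.1 and 1/119 = 0.8, using the planned sizes. The number actually treated is not in the documents.

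With 95% Clopper-Pearson intervals and illustrative counts:
- 7/26 = 26.9% (11.6 to 47.8) against 8/26 = 30.8% (14.3 to 51.8)
- 2/26 = 7.7% (0.9 to 25.1) against 3/26 = 11.5% (2.4 to 30.2)

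**The case against.** **The intended reading is already visible.** Section 10.5.3 says iRECIST has no separate assessment before RECIST 1.1 progression, so later responses have their own category. DOR runs from response to progression. Treatment normally stops at PD, scheduled scans run to PD, and active follow-up ends at radiological PD. Section 10.5.2 uses almost the same window sentence for mRECIST, which suggests template text. All of this stands as evidence of intent. None of it is a rule that removes a post-PD response from RECIST 1.1 best overall response, and 10.5.1 writes out a window that a programmer would follow.

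**The rule may sit elsewhere.** SAP v2.0 holds the main analytical approach, and the central reading rules are in a separate document. This stands. A reader might infer that the ORR already analysed includes such cases. The documents do not show that; they show only that the supplied text lacks the cut.

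**The written window does not err only upward.** A reader might infer that it can only overstate ORR. That is true only against the same window with an earlier stop. Section 8.1 continues scans after treatment stops without PD, and the end-of-intervention limit excludes a response first seen on those scans. Against a window running to PD or new therapy regardless of treatment, the written one could therefore miss responders.

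**Two further inferences fail.** SAP 5.7.1 takes the best percentage reduction over all tumor assessments, but that variable feeds a listing and waterfall plot, not best overall response. Nor can the point be turned into a type I error for 27/93 or 34/119. The share of such participants is unknown, the SAP version history says recruitment stopped early, and SAP 5.8 marks interim analyses as not applicable.

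**Conclusion.** The point holds for the text as supplied. Followed literally, the protocol counts a confirmed response after a reversed target-sum PD in the primary central ORR, while its own structure places that response in an exploratory iRECIST endpoint. It should be fixed, with medium confidence that it affects any result.

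The effect is probably small. It is bounded per participant at 3.8 points for a cohort of 26 and 1.9 points for the pilot total of 52. It falls on the reported ORR, its confidence interval and the DOR listing. The conclusion assumes that SAP v2.0 and the central review rules contain no cut at PD. If they do, what remains is a documentation mismatch in 10.5.1.

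**What to change.** First check SAP v2.0 and the central imaging review rules. If they already stop best overall response at first PD, align 10.5.1 with them and say so.

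Otherwise, keep the existing window and add earlier stops. In the SAP, and in 10.5.1 if the protocol is amended, state that RECIST 1.1 best overall response, for ORR and for identifying responders in DOR, uses assessments from start of intervention to the earliest of:
- end of intervention;
- first RECIST 1.1 PD by the same assessor (central for the primary endpoint, investigator for the secondary ones);
- start of new anti-cancer therapy, which under 4.1.1.3 and 8.1 already ends active follow-up and imaging.

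Later responses count only under iRECIST. In this form the change only removes assessments, so ORR can only fall or stay the same, and no new reads are needed.

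Decide separately whether off-drug scans before PD (section 8.1) should count. Admitting them could raise ORR and might need extra central reads, so it should not be folded into this change.

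The cost is one SAP sentence and a re-derivation from existing reads. Because SAP 5.3.1 shows the endpoint has already been analysed, this is a post-hoc clarification. Disclose it in SAP Appendix 2, which now reads as not applicable, and report the number of participants reclassified, including zero, with both ORR values if any change.

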5.1 Inclusion Criteria

Inclusion criteria must be met at the time of screening unless otherwise specified.

Participants are eligible to be included in the study only if all of the following criteria apply:

Age

1. \geq 18 years of age on the day of signing informed consent.

Type of Participant and Disease Characteristics

- 2. Histological or cytological confirmation of HCC or non-invasive diagnosis of HCC as per American Association for the Study of Liver Diseases (AASLD) criteria (see Appendix 11, Section 10.11) in cirrhotic participants.
- 3. Unresectable advanced HCC eligible for systemic therapy.
- 4. Participants must have progressed after only one prior line of systemic immunotherapy treatment with an anti-PD-1/PD-L1 mAb administered either as monotherapy or in combination with other checkpoint inhibitors or other therapies (for prior therapy in the cohorts in the pilot phase see Section 4.1). A wash out period of at least 28 days or 5 half-lives, whichever is shorter, must be completed for eligibility in this trial. PD-1/PD-L1 treatment progression is defined by meeting all of the following criteria:
 - a. Has received at least 2 doses of an approved anti-PD-1/PD-L1 mAb or received PD-1/PD-L1 treatment for 8 weeks, whichever is longer.
 - b. Has demonstrated disease progression after PD-1/PD-L1 treatment as defined by RECIST 1.1 (see Appendix 5, Section 10.5.1). In the absence of rapid clinical progression, the initial evidence of RECIST 1.1 disease progression is to be confirmed using iRECIST (see Appendix 5, Section 10.5.3) by a second assessment no less than four weeks from the date of the first documented progressive disease.
 - i. This determination is made by the investigator. Once progressive disease is confirmed, the initial date of RECIST 1.1 progressive disease documentation will be considered that date of disease progression.
 - ii. In cases of unequivocal clinical or radiological progression, disease progression confirmation may not be required after documented discussion and approval by the sponsor.
 - c. Progressive disease has been documented within 12 weeks from the last dose of anti-PD-1/PD-L1 mAb.

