 - o If the investigator considers radiographic changes secondary to drug-induced inflammation and not to tumor progression (i.e. in case of suspected pseudoprogression), the investigator may postpone a diagnosis of progressive disease until the next radiographic evaluation in the study, as per the criteria outlined in Appendix 10.5 in Section 10.5.3.
- Withdrawal of study intervention for abnormal liver function should be considered by the investigator when a participant meets one of the conditions outlined in Table 6–3 or if the investigator believes that it is in best interest of the participant.
- If a clinically significant electrocardiogram (ECG) finding is identified (including, but not limited to changes from baseline in QT interval corrected using Fridericia's formula [QTcF]) after enrollment, the investigator or qualified designee will determine if the participant can continue in the study and if any change in participant management is needed. This review of the ECG printed at the time of collection must be documented. Any new clinically relevant finding should be reported as an AE.

See the SoA (Section 1.3.1) for data to be collected at the time of intervention permanent discontinuation and follow-up and for any further evaluations that need to be completed.

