9.4.1.3 Secondary Efficacy Endpoints

The secondary efficacy endpoints in this study are DOR as per RECIST 1.1 by investigator assessment and central review and ORR as per RECIST 1.1 by investigator assessment.

DOR (for PR and CR) is defined as the time (in days) from the first documented objective response of PR or CR, whichever is noted earlier, to disease progression or death (if death

Page 95 of 141

occurs before progression is documented). DOR will be defined for responders only, i.e. participants with a CR or PR. The actual dates the tumor scans were performed will be used for this calculation. DOR for participants who have not progressed or died at the time of analysis will be censored at the date of their last tumor evaluation.

The analysis will be done on the Full Analysis Set. In the pilot phase, the analysis will be done by cohort. In the expansion phase, the analysis will be done on participants who received the first line treatment determined in the pilot phase of the study.

For analyses of the secondary endpoints, proportion-based efficacy variables will be using frequency tables as well as 95% two-sided Clopper-Pearson confidence intervals. With regard to time to event data, these will be summarized descriptively using Kaplan Meier methodology and plots, as well as median estimates based on Greenwood's formula, including 95% two-sided confidence interval.

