The following text descriptions of the visit response are logically equivalent to the tables below.

Any

Anv

Page 123 of 141

Target Lesions	Non-Target Lesions	New Lesions	Overall Response	Best Response for this category also requires
CR	CR	No	CR	
CR	Non-CR/Non-PD	No	PR	
CR	Not evaluated	No	PR	
PR	Non-PD or not all evaluated	No	PR	
SD	Non-PD or not all evaluated	No	SD	Documented at least 6 weeks from treatment allocation.
Not all evaluated	Non-PD	no	NE	
PD	Any	Yes or No	PD	
Any	PD	Yes or No	PD	

Table 10-9: Response for Participants with Target and Non-target Lesions

Yes

PD

Table 10–10: Response for Participants with Non-target Lesions Only

Non-Target Lesions	New Lesions	Overall Response
CR	No	CR
Non-CR/Non-PD	No	Non-CR/non-PD*
Not evaluated	No	NE
Unequivocal PD	Yes or No	PD
Any	Yes	PD

CR = complete response; NE = non-evaluable; PD = progressive disease

10.5.3 iRECIST

iRECIST is RECIST 1.1 adapted as described below to account for the unique tumor response seen with immunotherapeutic drugs (Table 10–11). If the investigator considers radiographic changes secondary to drug-induced inflammation and not to tumor progression (i.e. in case of suspected pseudo-progression), the investigator may postpone a diagnosis of progressive disease until the next radiographic evaluation in the study, and further confirmation per iRECIST criteria. This decision by the investigator should be based on the participant's overall clinical condition.

Description of the iRECIST Process for Assessment of Disease Progression

Assessment at Screening and Prior to RECIST 1.1 Progression

Until radiographic disease progression based on RECIST 1.1, there is no distinct iRECIST assessment.

Assessment and Decision at RECIST 1.1 Progression

For participants who show evidence of radiological PD by RECIST 1.1, the investigator will decide whether to continue a participant on study intervention until repeat imaging is obtained

CR = complete response; NE = non-evaluable; PD = progressive disease; PR = partial response; SD = stable disease

Participants with a global deterioration of health status requiring withdrawal of intervention without objective evidence of disease progression at that time should be reported as "symptomatic deterioration". Every effort should be made to document the objective progression even after withdrawal of intervention.

^{*} Non-CR/non-PD is preferred over "stable disease" for non-target disease.

Page 124 of 141

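### Two protocol sentences let the investigator postpone the PD diagnosis itself, which conflicts with the RECIST 1.1 rules and leaves the PD date for investigator-assessed DOR and PFS open

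*Protocol*

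**What the plan says.** **The permission.** Protocol Section 10.5.3 opens with a condition: "If the investigator considers radiographic changes secondary to drug-induced inflammation and not to tumor progression". The investigator then "may postpone a diagnosis of progressive disease until the next radiographic evaluation in the study, and further confirmation per iRECIST criteria". Section 7.1.1.1 repeats this in a sub-item under the exception for continuing treatment: "the investigator may postpone a diagnosis of progressive disease until the next radiographic evaluation in the study, as per the criteria outlined" in the appendix.

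**The RECIST 1.1 rules.** Section 10.5.1 calls PD on a 20% and 5 mm increase from the smallest sum, on unequivocal non-target progression, or on a new lesion. It asks for no confirmation and has no exemption for pseudo-progression. Response lasts until PD is first objectively documented.

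**The rest of Section 10.5.3.** RECIST 1.1 PD comes first: "Until radiographic disease progression based on RECIST 1.1, there is no distinct iRECIST assessment". Then, for iRECIST purposes, "the first visit showing progression according to RECIST 1.1 will be assigned a visit (overall) response of iUPD". What the investigator decides at that point is whether treatment continues.

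**The endpoints.** Section 9.4.1.3 lists "DOR as per RECIST 1.1 by investigator assessment and central review" as secondary and dates events by the actual scan dates. Table 3-1 makes investigator RECIST 1.1 PFS exploratory and lists separate exploratory iRECIST ORR and DOR. In SAP v3.0, DOR is only listed (5.4.1.2). PFS gets Kaplan-Meier estimates and rates at 6, 12, 18 and 24 months (5.5.2). Endpoint definitions are referred to SAP v2.0.

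**The concern.** What may be postponed is the diagnosis, not the action that follows from it. Continuing treatment past RECIST 1.1 progression is already allowed elsewhere (Sections 4.1.1.2, 6 and 7.1.1.1, and later in 10.5.3). Read as a treatment permission only, the sentence would add nothing, so a site has reason to read it as written and enter something other than PD at the first qualifying scan.

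The investigator RECIST 1.1 DOR and PFS would then follow iRECIST timing for some participants and RECIST 1.1 timing for others, according to each investigator's belief about pseudo-progression in an open-label, single-arm trial. The error runs mostly one way, towards longer times. It would also blur the comparison with the central RECIST 1.1 results and with the separate iRECIST DOR.

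**Working it through.** **1. The plan's own figures.** The only design calculation concerns the primary endpoint, centrally assessed ORR. By exact binomial:
- P(X ≥ 27 | n = 93, p = 0.20) = 0.0238
- P(X ≥ 34 | n = 119, p = 0.20) = 0.0158
- Conditional power at 35%, given at least 8/26 in cohort 1: 0.955
- Conditional power at 35%, given at least 8/26 in each cohort: 0.990

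These agree with Section 9.2 (one-sided 0.025, at least 95%). No investigator PD date enters them.

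**2. The texts side by side, for one scan that meets PD criteria with suspected pseudo-progression.**

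| Text followed | Investigator RECIST 1.1 entry at that scan |
|---|---|
| 10.5.1 (PD definition, end of response) | PD |
| 10.5.3, iUPD paragraph | PD, with iUPD as the iRECIST label |
| 10.5.3 opening sentence and 7.1.1.1 sub-item, read literally | PD not yet called |

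Section 9.4.1.3 uses actual scan dates but does not say which scan counts when the diagnosis was postponed. The protocol writes a rule keeping the first date in two other places. For prior-therapy progression, inclusion criterion 4 says "the initial date of RECIST 1.1 progressive disease documentation will be considered that date of disease progression". For mRECIST, Section 10.5.2 dates an event back to first detection. Neither covers on-study RECIST 1.1 PD.

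**3. Delay per affected event.** Inputs are the repeat scan at 4 to 8 weeks (10.5.3, Table 10-11) and scheduled scans every 6 weeks to week 54, then every 9 weeks, each ±7 days (Section 8.1). The delay is 4 to 8 weeks with the repeat scan, or about 6 or 9 weeks at the next scheduled scan. It is longer if iUPD persists. If iUPD resolves, the event is not recorded until a later PD, death or censoring.

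Example: PR at weeks 12 and 18, new lesion at week 30, worse at week 36.
- First qualifying scan: 30 − 12 = 18 weeks.
- Postponed date: 36 − 12 = 24 weeks.

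**4. Mean shift.** Formula: share postponed × delay. The documents give no share, so 5% to 30% is an assumption.

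| Share | 4 weeks | 6 weeks | 8 weeks | 9 weeks |
|---|---|---|---|---|
| 5% | 0.20 | 0.30 | 0.40 | 0.45 |
| 10% | 0.40 | 0.60 | 0.80 | 0.90 |
| 20% | 0.80 | 1.20 | 1.60 | 1.80 |
| 30% | 1.20 | 1.80 | 2.40 | 2.70 |

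Events that go unrecorded because iUPD resolved are not included.

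**5. Check by simulation.** 400,000 exponential times to PD were read at the next scheduled scan, with 20% moved one scheduled scan later. Assumed true medians of 12, 18 and 26 weeks gave means of 20.51 → 21.75, 29.26 → 30.56 and 41.01 → 42.38. The rises are 1.24, 1.30 and 1.37 weeks, inside the 1.2 to 1.8 range in step 4.

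**6. Landmark rates.** Six months is 6 × 365.25 / (12 × 7) = 26.1 weeks. A PD at the week 24 scan falls before it. Postponed to week 30, or to a repeat scan at weeks 28 to 32, it falls after, and the participant counts as progression-free at 6 months.

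**The case against.** The strongest reply is that RECIST 1.1 dating is already settled. Section 10.5.1 has no exemption, Table 10-5 makes any new lesion PD, and RECIST 1.1 PD must exist before iRECIST starts. Section 8.1 confines iRECIST to treatment-related decisions and exploratory analyses. The Section 7.1.1.1 sentence sits under a treatment exception. On this view, diagnosis is a loose word for the decision to stop.

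Much of this stands. A reader might infer that the protocol itself sets the later date, so that DOR in the example is 24 weeks as written. The documents do not support that: under Sections 10.5.1 and 9.4.1.3 together it is 18 weeks, and 24 arises only if a site acts on the postponement sentence. The permission is also optional and limited to suspected drug-induced inflammation, so a calculation that postpones every PD has no basis. Nor is a 9-week step the general case, given the 4 to 8 week repeat scan for participants who continue treatment.

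A reader might also take the back-dating in criterion 4 as proof that its absence elsewhere was deliberate. It is not: that criterion normally requires a confirmatory scan, so a dating rule was needed there, whereas on-study RECIST 1.1 PD needs no confirmation.

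What the reply does not remove is the sentence itself, written twice, which a site can follow in good faith against Section 10.5.1. Nor does it supply a rule for the resulting date.

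**Conclusion.** The point holds as a conflict in the text that creates a risk, not as a rule that moves the PD date. An affected event can move by 4 to 8 weeks with the repeat scan, by about 6 or 9 weeks with the next scheduled scan, or go unrecorded if iUPD resolves. At an assumed 5% to 30% share and one scheduled scan of delay, the mean shift is roughly 0.3 to 2.7 weeks. The true share is unknown and could be near zero.

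The scope is investigator-assessed RECIST 1.1 DOR and PFS. Primary central ORR, its decision rules and power are untouched. Central DOR and PFS are also unaffected, since the sentences address the investigator's assessment. No effect on investigator ORR has been shown.

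Two facts limit the consequence further: recruitment stopped early (SAP version history), and the final analysis only lists DOR. SAP v2.0, which was not supplied, may contain a dating rule, so its absence cannot be asserted; Protocol Section 9.4 and SAP v3.0 contain none.

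**What to change.** - **Protocol Sections 7.1.1.1 and 10.5.3:** reconcile the two postponement sentences with Section 10.5.1 and the iUPD paragraph, so that the RECIST 1.1 assessment at the first scan meeting PD criteria is recorded as PD whatever iRECIST later shows. Leave the treatment-continuation provisions and the scan schedule as they are.
- **Protocol Section 9.4.1.3 and the SAP:** state that investigator RECIST 1.1 DOR and PFS use that scan date, and that iRECIST dates serve only the iRECIST endpoints. If SAP v2.0 already says this, refer to it.
- **eCRF completion guidance:** add the same instruction.

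The cost is a few sentences. Because Section 8.1 has site measurements and assessments entered in the eCRF, the analysis can apply the rule to data already collected, at least for target-lesion growth and recorded new lesions. The downside is that investigator DOR and PFS may read slightly shorter.
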